# **Drug Destruction and Return**

When all patients have completed treatment at your institution, all unused, partially used, expired or empty containers must be destroyed at the site according to the institution's policy for drug destruction. Please maintain appropriate records of the disposal, including dates and quantities. Sites are required to complete the Certificate of Destruction Form located in Appendix V. A copy of this form should be sent to iits [contact].

# **Drug Inventory Records**

Investigational Product Records at Investigational Site(s): It is the responsibility of the Investigator to ensure that a current record of investigational product disposition is maintained at each study site where investigational product is inventoried.

Please note that expiration dates are not listed on the vials. Lot numbers and related expiration dates are listed on the Drug Product Request Shipment Form which is shipped with the vials. Sites should keep a copy of this form as part of their drug inventory records.

# 8.3.10 Side Effects

Adverse events of concern, which may or may not be associated with IMC-1121B therapy, include infusion reactions, hypertension, arterial or venous thrombotic events, proteinuria, bleeding, headache and fatigue.

# 8.3.11 Nursing/Patient Implications

- 1. Monitor patient closely during infusion, for infusion related events.
- 2. Monitor blood pressure prior to each dose to assess for development of hypertension.

Rev. 12/11

Rev. 5/16

Rev. 7/12

- 3. Instruct patient to monitor and report signs/symptoms of: bleeding (nose bleeds, blood in sputum), wound healing problems, abdominal pain, thromboembolic problems (chest or leg pain, dyspnea, vision changes, severe headache, cough, swelling)
- 4. Baseline urine protein must be performed and repeated every six weeks. If elevated, 24 hour urine collection must be performed.
- 5. Treat pain, arthralgias, etc. with acetaminophen, or other pain relief strategies that do not interfere with the clotting cascade.

# Safety Precautions

Appropriate mask, protective clothing, eye protection, gloves, and Class II vertical-laminar-airflow safety cabinets are recommended during preparation and handling. Opened vials must be disposed of at the investigational center as chemotherapy or biohazardous waste provided documented procedures for destruction are in place. For questions regarding IMC-1121B destruction please contact Lilly at iits\[contact].

IMC-1121B therapy should be used with caution in patients with known hypersensitivity to cetuximab, murine proteins, or any component of this product.

It is recommended that patients wear sunscreen and hats and limit sun exposure while receiving IMC-1121B as sunlight can exacerbate any skin reactions that may occur. 9.1

# 9. Statistical Considerations

Rev. 6/14, 6/14

# Safety Monitoring

Revised Statistical Design - Arms A (IC) and C (mICR)

The revised investigational regimen (that is, Arm C (mICR), a revision of the previous investigational Arm B) will be examined among the first 16 patients enrolled to Arm C post the re-activation of the randomized trial. Randomization will commence to Arms A and C and for purposes of adverse event evaluation, close monitoring of the study will occur until 16 patients have been enrolled to Arm C and followed through 2 cycles of therapy. During this safety evaluation period all patients will be followed closely with monthly conference calls of the study team and independent toxicity monitor to review all real-time CTEP-AERS reports and any case report form reported treatment-related adverse events. At the time of suspension of this study prior to reactivation, the accrual rate was about 3-4 patients per month. Given this expected recruitment pattern upon initially re-opening the study, it appears reasonable to have calls on a monthly basis. Once fully reactivated, the accrual rate should be 10 patients per month. If the accrual pattern is substantially higher during the first few months after reactivation, the study team will convene calls every two weeks.

The toxic death rate on Arm B (ICR) prior to study suspension was 2/16 patients or 12.5%. With 16 patients on Arm C (mICR) evaluated under the new regimen the probability of observing 1 or more toxic deaths is 81.5% if the true toxic death rate is 10% and 88.2% under a true toxic death rate of 12.5%. No toxic deaths were observed in Arm A prior to suspension among 17 treated patients. Under the revised design with 16 patients evaluated on Arm C (mICR) the probability of observing one or more toxic deaths under a true toxic death rate of 0.77% is 11.6%. If one or more toxic deaths occur at any point during the 16 patient evaluation of Arm C, the study will close to accrual and the regimen will be abandoned.

The safety evaluation will also closely assess all treatment-related toxicities other than those of grade 5 with a particular emphasis on evaluating grade 3 and 4 events. Prior to suspension the grade 3 or higher treatment-related adverse event rate on Arm A was 16.7%. With 16 patients on Arm C there is 81% power to detect a true grade 3 or higher toxicity rate of 39% (versus a null of 16.7%) and 90% power to detect a true rate of 44% using a one-sided exact binomial test at the 11% significance level (evaluating Arm C separately as the power for the two-group comparison is limited). The observed grade 3 or higher toxicity rate on Arm B was 87.5%. If the grade 3 or higher toxicity test is significant after 16 patients on Arm C, the study will suspend accrual and the feasibility of the revised regimen will be evaluated by the study team and independent toxicity monitor, including a detailed review of all grade 3 or higher treatment related events. In addition to the above safety monitoring plan, the study will suspend upon the report of any colonic perforation event, regardless of treatment attribution or grade. A detailed review of the circumstances surrounding the event will be conducted and, in the case of the event occurring on Arm C, the feasibility of the revised regimen will be evaluated by the study team and toxicity monitor. The colonic perforation rate on Arm B (ICR) prior to study suspension was 2/16 patients or 12.5%. With 16 patients on Arm C (mICR) evaluated under the new

Rev. 6/14

Rev. 6/14

regimen the probability of observing 1 or more colonic perforations is 81.5% if the true rate is 10% and 88.2% under a rate of 12.5%. No toxic deaths were observed in Arm A prior to suspension among 17 treated patients.

In addition, the evaluation of 16 patients randomized to Arm C will allow estimation of any given toxicity with a 90% confidence interval that is no wider than 44.3 percentage points and there is 56.0% probability of observing any given event (1 or more out of 16 patients) with a true frequency of 5% and 81.5% probability observing 1 or more events with true frequency of 10%.

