## 1.6 Summary of Toxicity Review

The study was closed to accrual on June 14, 2012 after 35 registrations were accrued as per pre-planned toxicity review. 18 patients (17 treated: one case never started assigned therapy) were accrued to Arm A (IC) and 17 (16 treated: one case was a duplicate registration) to Arm B (ICR). AdEERS Reporting was reviewed and real time data were obtained on all treated patients. It was clear that more toxicity was seen in Arm B. Worst toxicity per patient is seen in the figure below. The overall grade 3-5 toxicity rates were 17% for Arm A and 75% for Arm B. There were 2 toxic deaths in Arm B. Toxicities of higher incidence in Arm B included neutropenia, mucositis, diarrhea and GI perforation (including peri-anal abscess). In addition mean dose given in Arm B (mean % RDI) was considerably lower in Arm B: 65% for irinotecan, 85% for cetuximab and 92% for ramucirumab (even though no dose reductions were allowed in the protocol). This compares to 99% irinotecan and 98% cetuximab average %RDI in Arm A. Furthermore, only 3/17 patients in Arm A required dose reduction, compared to 15/16 in Arm B. On the other hand with a median of 8 cycles preliminary analysis showed that fewer patients in Arm B went off treatment for progression compared with Arm A, and more remained on treatment at the time of the analysis. Of the 17 treated in Arm A, 8 out of 9 patients off study had progression (PD), while in Arm B, of the 16 treated, only 1 out of 5 who went off study, went off for PD. These findings suggest potential benefit for the addition of ramucirumab among patients who can tolerate therapy. Therefore, we propose a reduced dose regimen in Arm C (modified ICR) with irinotecan 150 mg/m^2, cetuximab 400  $mq/m^2$  and ramucirumab 6  $mq/m^2$  as starting doses, more strict eligibility criteria, and more aggressive dose modifications for toxicity. Because those patients on protocol who did tolerate the ICR regimen at the reduced doses seemed to stay on study longer, we believe the study should be continued as modified at those lower doses. The Arm C starting doses are equal to the actual "percent recommended dose intensity" received by patients in Arm B.

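### The Arm C safety run-in tests the grade 3 or higher rate against an Arm A null without giving both sides the same exposure window, so the stated 11% level and 81%/90% power are not assured.

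*Combined protocol and SAP*

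**What the plan says.** All references are to the combined protocol and SAP.

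- Section 9.1, Safety Monitoring, sets the length of the run-in: "close monitoring of the study will occur until 16 patients have been enrolled to Arm C and followed through 2 cycles of therapy". During it, the study team and the independent toxicity monitor meet "to review all real-time CTEP-AERS reports and any case report form reported treatment-related adverse events".
- The null of the grade 3 or higher test comes from Arm A: "Prior to suspension the grade 3 or higher treatment-related adverse event rate on Arm A was 16.7" per cent. The test is a one-sided exact binomial test at 11% on 16 patients, with "81% power to detect a true grade 3 or higher toxicity rate of 39% (versus a null of 16.7" per cent) and "90% power to detect a true rate of 44" per cent. A significant result suspends accrual for a feasibility review.
- The toxic-death closure rule is worded "If one or more toxic deaths occur at any point during the 16 patient evaluation of Arm C". Section 9.1 gives the chance of at least one such death among 16 as 81.5%, 88.2% and 11.6% for true rates of 10%, 12.5% and 0.77%. The 12.5% is Arm B's history: "The toxic death rate on Arm B (ICR) prior to study suspension was 2/16 patients or 12.5" per cent.
- Section 1.6 reports overall grade 3-5 rates of 17% (Arm A) and 75% (Arm B), in a review of worst toxicity per patient using data on all treated patients. The same paragraph says that "with a median of 8 cycles preliminary analysis showed that fewer patients in Arm B went off treatment for progression".
- Section 9.2 had planned the toxicity review of the original design on forms through cycle 2.

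**The concern.** A rate of patients with any grade 3 or higher event rises with the time over which they are watched. A binomial test of one such rate against another is calibrated only if both cover the same exposure. Section 9.1 guarantees two 14-day cycles for the last Arm C entrants. It does not say which Arm C cycles count, or which cycles lie behind the 16.7%.

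The protocol itself gives reason to expect some later toxicity. Section 1.4.1 says that the dose-limiting toxicities of weekly ramucirumab appeared after several cycles. Section 7 schedules urine protein every 6 weeks, so the first on-treatment test falls after a 28-day window.

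At stake is the decision that the run-in exists to make. If exposure differs, the same count of 5 in 16 can be too hard or too easy to reach, and the stated error rates describe no defined test.

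**Working it through.** **Inputs.** n = 16, null 16.7%, alternatives 39% and 44%, level 11%, accrual 3-4 per month on reopening and 10 per month later (Section 9.1); equal randomization, so half of each rate goes to Arm C; 14-day cycles (Section 5.1); median 8 cycles (Section 1.6). Event timing is not in the documents. The timing models below are assumptions.

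**1. Reproduce the plan.** P(X ≥ r) = Σ over k ≥ r of C(16,k) p^k (1−p)^(16−k). The critical count is not stated. At p = 0.167, r = 4 gives 0.272, r = 5 gives 0.114 and r = 6 gives 0.038, so the rule is 5 or more of 16. With r = 5, power is 0.812 at 39% and 0.902 at 44%, as stated. For deaths, 1 − (1−p)^16 gives 0.815, 0.882 and 0.116 at 10%, 12.5% and 0.77%, as stated.

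**2. Only cycles 1-2 count, and the null covers about 8 cycles.** P is the full-course rate. With a fixed share f of first events by cycle 2, p = fP. With constant hazard, p = 1 − (1−P)^(2/8). The rule stays at 5 of 16.

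| Timing | Null becomes | Actual level | 39% becomes | Power | 44% becomes | Power |
|---|---|---|---|---|---|---|
| f = 1 (as stated) | 0.167 | 0.114 | 0.390 | 0.81 | 0.440 | 0.90 |
| f = 0.90 | 0.150 | 0.080 | 0.351 | 0.71 | 0.396 | 0.83 |
| f = 0.75 | 0.125 | 0.041 | 0.293 | 0.52 | 0.330 | 0.65 |
| Constant hazard | 0.045 | 0.0005 | 0.116 | 0.03 | 0.135 | 0.05 |

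**3. All events to date count.** Assume even entry and no early discontinuation. Patient i (i = 0 to 15) then has c_i = 2 + [(15 − i)/a] × 30.44/14 elapsed cycles when the last entrant completes cycle 2, where a is Arm C accrual per month.

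- a = 5 (10 per month in total): median 5.3 cycles, range 2 to 8.5.
- a = 1.5 to 2 (3-4 per month): median 12.9 to 10.2 cycles, range 2 to 23.7 or 18.3.

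Each patient has probability p_i = 1 − (1−P)^(c_i/8) under constant hazard. For share f by cycle 2 with the rest spread evenly to cycle 8, p_i = P[f + (1−f)(min(c_i,8) − 2)/6]. The chance of 5 or more is the upper tail of the sum of 16 independent indicators with these p_i. At P = 39%:

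| Timing | 10 per month | 3-4 per month |
|---|---|---|
| Constant hazard, exposure capped at 8 cycles | 0.44 | 0.68-0.71 |
| Constant hazard, no cap | 0.45 | 0.92-0.98 |
| f = 0.75 | 0.70 | 0.77-0.78 |
| f = 0.90 | 0.77 | 0.79-0.80 |

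In the uncapped case at 3-4 per month, an Arm C regimen whose 8-cycle rate is exactly 16.7% would trigger suspension 20-35% of the time, against the stated 11%. The mismatch then works against Arm C.

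**4. Source rates.** 16.7% is 3/18, but Section 1.6 counts 18 accrued and 17 treated on Arm A, and 3/17 = 17.6%. For Arm B, 75% is 12/16 (Section 1.6) and 87.5% is 14/16 (Section 9.1).

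**The case against.** The strongest reply is that two cycles mark when the run-in ends, and are not a cut-off for counted events. The review takes in all expedited and case-report-form events, and the death rule runs throughout the evaluation. Patients who enter early are watched for longer, and at the 3-4 per month expected on reopening, median elapsed time exceeds 8 cycles. The 8-cycle figure stands in a sentence about leaving treatment for progression, and Section 9.2 planned that review through cycle 2, so the window behind 16.7% is unknown. All of this stands. It removes any claim of a known direction, but does not supply the missing windows.

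A reader might infer three stronger things that the documents do not support:

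- **That the test is certainly biased toward passing Arm C.** This needs a cycle-2 cut-off, or fast accrual, together with a null known to cover a longer course. Neither is established.
- **That Arm B's rates are benchmarks of the test.** Only Arm A's 16.7% enters it. The death and perforation rules act on a single event, and Arm B's rates illustrate detection probabilities.
- **That late perforations or deaths go unwatched.** The perforation rule is not limited to the run-in and needs no change. Sections 9.1 and 9.3 also provide twice-yearly toxicity analyses, monthly notification of all grade 5 events and data monitoring committee review. What is unclear is only how long the automatic toxic-death closure covers the 16 run-in patients.

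**Conclusion.** The point holds as an undefined and probably unequal exposure window. The arithmetic in Section 9.1 is correct, but its 11% level and 81%/90% power apply only if the Arm C count and the 16.7% null cover the same cycles, which no passage secures.

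If the null reflects about 8 cycles, power at 39% is 3% to 71% under a cycle 1-2 count, for timings from constant hazard to 90% of first events by cycle 2. Under an all-events count at 10 per month it is about 45% (constant hazard) to 70% (75% by cycle 2), reaching 77% at 90% by cycle 2. At 3-4 per month it lies on either side of the stated value. If nearly all first events occur by cycle 2, or if 16.7% is itself a cycle 1-2 rate matched by a cycle 1-2 count, the stated figures are about right. These results rest on assumed timing, even entry and no early discontinuation; early discontinuation would shorten the exposure in step 3.

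This should be corrected, because it bears on a suspension decision and the data needed are already held.

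**What to change.** - State in Section 9.1 one event window for both sides. Re-tabulate the existing Arm A grade 3 or higher rate over the window used for Arm C, for example cycles 1-2.
- Restate the null, critical count, level and power for that window, and say that the 81.5%, 88.2% and 11.6% toxic-death probabilities refer to it.
- Reconcile the Section 9.1 passages that bear on how long the toxic-death closure rule covers the 16 run-in patients.
- Reconcile the source rates: 3/18 against 17 treated on Arm A, and 75% against 87.5% on Arm B.

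The cost is a re-tabulation and a few sentences, with no added visits. The stated power may look worse. For example, if 75% of first events fall by cycle 2, the null is 12.5%. Then 4 or more of 16 gives a level of 13.1% with 73% and 83% power at the matching rates of 29.3% and 33%, and 5 or more gives 4.1% with 52% and 65%. Those would at least be the properties of the test actually performed.

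### The Arm C grade 3 or higher suspension test in section 9.1 prints no count: its stated power belongs to 5 or more of 16 (exact level 11.4%), but a test held literally to 11% needs 6 of 16, with power of only 64% and 78%

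*Combined protocol and SAP*

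**What the plan says.** The safety monitoring text of section 9.1 (revised design, Arms A and C) takes its null from the control arm: "Prior to suspension the grade 3 or higher treatment-related adverse event rate on Arm A was 16.7" percent. It then gives the operating characteristics: "With 16 patients on Arm C there is 81% power to detect a true grade 3 or higher toxicity rate of 39" percent, and 90% power at a true rate of 44%, "using a one-sided exact binomial test at the 11% significance level". The consequence follows: "If the grade 3 or higher toxicity test is significant after 16 patients on Arm C, the study will suspend accrual". The study team and the independent toxicity monitor then review the feasibility of the regimen.

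Neither section 9.1 nor any other section gives the number of patients with events at which this test is significant. The other toxicity rules do give one. In 9.1, a single toxic death during the 16-patient evaluation closes the study, and a single colonic perforation suspends it. In 9.2, the original design set its grade 4 or worse trigger at four or more patients and its toxic death trigger at one or more.

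**The concern.** With 16 patients an exact binomial test can attain only a few levels, so the boundary has to be a whole number. Anyone applying the rule must work that number out from the level or from the power, and the two routes give different answers.

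A statistician who compares the exact p-value with 0.11 would not suspend at 5 of 16. One who works back from the stated power would. At a true rate of 39%, exactly 5 of 16 occurs about 17% of the time, so the disputed outcome is a realistic one. This is also the formal check on a regimen redesigned because its predecessor, Arm B, was too toxic.

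**Working it through.** **Inputs.** All are from section 9.1: n = 16; null p0 = 0.167; alternatives 0.39 and 0.44; one-sided exact binomial test; stated level 11%; stated power 81% and 90%.

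**Formula.** For a boundary of r or more, the probability of suspension at true rate p is P(X ≥ r) = Σ from k = r to 16 of C(16,k) p^k (1−p)^(16−k).

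**Step 1: reproduce the stated power.**

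| Boundary | Level at 16.7% | Power at 39% | Power at 44% |
|---|---|---|---|
| 4 or more | 27.2% | 92.4% | 96.6% |
| 5 or more | 11.4% | 81.2% | 90.2% |
| 6 or more | 3.8% | 64.1% | 77.9% |

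Only 5 or more gives the printed 81% and 90%.

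**Step 2: the exact level of that rule.** At p0 = 0.167 the probabilities of 0, 1, 2, 3 and 4 events are 0.0537, 0.1724, 0.2592, 0.2425 and 0.1580. They sum to 0.8859, so P(X ≥ 5) = 0.114. Rounded to a whole percent this is the printed 11%.

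**Step 3: apply 11% as written.** At 5 of 16 the one-sided p-value is 0.114, above 0.11, so the test does not reject. At 6 of 16 it is 0.038 and the test rejects. A literal 11% test therefore has boundary 6, and its power falls by 81.2 − 64.1 = 17.1 points at 39% and by 90.2 − 77.9 = 12.3 points at 44%. The null would have to be 16.5% or lower for 5 or more to stay within 0.11.

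**Step 4: how often the two readings differ.** They differ only at exactly 5 of 16. That has probability 0.8123 − 0.6408 = 0.1715 at 39% and 0.9015 − 0.7792 = 0.122 at 44%.

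**Step 5: the Arm A count behind 16.7%.** Section 1.6 reports 18 patients accrued to Arm A, of whom 17 were treated, and an overall grade 3–5 rate of 17%. 3/18 = 16.7%. No count out of 17 gives that figure: 2/17 = 11.8% and 3/17 = 17.6%. The value therefore fits all accrued patients, including the one who never started therapy. If the count is 3 of 17 treated, the null becomes 17.6% and the level of 5 or more of 16 becomes 13.7%. Power at 39% and 44% is unchanged, because it does not depend on the null once the boundary is fixed.

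**The case against.** The strongest reply is that the rule can already be identified. Only one boundary fits both printed powers, and its attained level rounds correctly to 11%. The natural reading is that 11% reports that attained level. Reaching 6 of 16 means treating a rounded figure as an exact cap and ignoring two powers printed in the same sentence. This stands as far as it goes: a reader might infer that the level or the power was miscalculated, and the documents do not support that.

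A reader might also infer that patients are left less protected. They are not if 5 is used. Whichever count is applied, the test is backed by "monthly conference calls of the study team and independent toxicity monitor to review all real-time CTEP-AERS reports", by closure on a toxic death and by suspension on a colonic perforation. A significant result leads to suspension and review, not to automatic abandonment of the regimen.

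Three further inferences go too far:

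- **That the null has no stated basis.** Its source is stated: it is the Arm A rate before suspension. Only the numerator and denominator are missing from the text, and they may appear in the figure of worst toxicity per patient in section 1.6, which was not available for this review. That the count is 3/18 is an inference from arithmetic.
- **That the 16 patients are defined inconsistently.** They are described as enrolled in one place ("close monitoring of the study will occur until 16 patients have been enrolled to Arm C and followed through 2 cycles of therapy") and as randomized in another ("the evaluation of 16 patients randomized to Arm C will allow estimation"). Enrolment in this trial produces the randomization, so the two words do not conflict.
- **That the two Arm B rates undermine the test.** Section 1.6 gives 75% and section 9.1 gives 87.5%. The discrepancy is real, but neither figure enters the test.

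What remains is that the boundary is not printed, and that the stated level taken literally leads to a boundary without the stated power.

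**Conclusion.** The point holds, and it is minor. The stated level and the stated power agree only after rounding. Followed to the letter, the 11% test suspends at 6 of 16 and has power of 64% and 78%, not 81% and 90%. The boundary consistent with the plan's own power is 5 or more of 16, with exact level 11.4%.

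This rests on the 16.7% null and on 16 evaluated patients, both as printed. The possible move of the null to 17.6% and the level to 13.7% depends on a count that has still to be confirmed, and it does not alter the main conclusion.

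**What to change.** In section 9.1, state the boundary that underlies the printed power: accrual is suspended if 5 or more of the 16 Arm C patients have a treatment-related grade 3 or higher event; exact one-sided level 11.4% at a null of 16.7%; power 81% at 39% and 90% at 44%.

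Before printing it, confirm the Arm A count from the existing toxicity tables and give it as a numerator and denominator. If it is 3 of 17 treated, print a null of 17.6% and a level of 13.7% for the same boundary.

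Separately, reconcile the Arm B rates of 75% and 87.5%, giving the data cut and event definition for each.

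The cost is one sentence and one table check. No sample size or power is lost. The only downside is a slightly less favourable stated level. Applying the boundary as soon as a fifth event is reported, matching the observation window between arms, or replacing untreated patients would be optional design choices. None of them is needed to correct this point.

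### The Arm C grade 3+ toxicity test acts only after 16 patients, although its implied count of 5 can be reached earlier and no rule then requires suspension

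*Combined protocol and SAP*

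**What the plan says.** Section 9.1 (Safety Monitoring) sets up a 16-patient evaluation of Arm C: "close monitoring of the study will occur until 16 patients have been enrolled to Arm C and followed through 2 cycles of therapy". Three rules apply to it.

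- **Toxic death.** This acts immediately: "If one or more toxic deaths occur at any point during the 16 patient evaluation of Arm C", accrual closes and the regimen is dropped.
- **Colonic perforation.** The study suspends when any such event is reported, whatever its grade or attribution.
- **Grade 3 or higher treatment-related events.** This acts once: "If the grade 3 or higher toxicity test is significant after 16 patients on Arm C, the study will suspend accrual". A feasibility review follows. The null comes from Arm A: "Prior to suspension the grade 3 or higher treatment-related adverse event rate on Arm A was 16.7" per cent. The test is described as "using a one-sided exact binomial test at the 11% significance level", and its critical count is not given.

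Monthly calls (every two weeks if accrual is substantially faster) review adverse events during the evaluation. Section 9.1 attaches no grade 3-4 count to those calls.

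**The concern.** The number of Arm C patients with a qualifying event can only rise as more patients are treated, unless an event is reattributed or a record corrected. So the test can be settled well before patient 16. As written, randomisation to Arm C may then continue to 16, although the patients still to come cannot change whether the test is significant. Arm C exists because its predecessor was too toxic. Section 1.6 puts the grade 3-5 rate on Arm B at 75% and Section 9.1 gives 87.5%. At stake are patients randomised after the plan's own signal for suspension has been met.

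**Working it through.** **Inputs.** From Section 9.1: n = 16; null 16.7%; alternatives 39% and 44%; Arm B grade 3+ rate 87.5%; Arm B toxic deaths 2/16 and colonic perforations 2/16 (12.5% each); accrual of 3-4 per month at first and 10 per month when fully reactivated, over two equal arms, so 1.5-2 or 5 Arm C patients per month. From Section 1.6: Arm B grade 3-5 rate 75%. Two 14-day cycles make a 28-day window.

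**Step 1: reproduce the stated power.** The plan says "there is 81% power to detect a true grade 3 or higher toxicity rate of 39% (versus a null of 16.7" per cent) and "90% power to detect a true rate of 44" per cent. With X ~ Binomial(16, p), P(X ≥ c) is:

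| c | p = 0.167 | p = 0.39 | p = 0.44 |
|---|---|---|---|
| 4 | 0.272 | 0.924 | 0.966 |
| 5 | 0.114 | 0.812 | 0.902 |
| 6 | 0.038 | 0.641 | 0.779 |

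Only c = 5 gives 81% and 90%, and its alpha of 0.114 is 11% to the precision stated. A strict cap of 0.11 would require c = 6, which contradicts the stated power.

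**Step 2: acting early does not alter the test.** A fifth patient with an event at or before patient 16 is the same outcome as 5 or more of 16. Alpha stays 0.114 and power stays 0.812 and 0.902.

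**Step 3: patients enrolled after the result is fixed, with no lag and no other rules.** The fifth event falls at patient k with probability C(k−1, 4) p^5 (1−p)^(k−5), for k = 5 to 16. The remainder is 16 − k.

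| True rate | P(cross) | Mean k given crossing | Remaining given crossing | Remaining, unconditional |
|---|---|---|---|---|
| 39% | 0.812 | 11.2 | 4.8 | 3.9 |
| 44% | 0.902 | 10.5 | 5.5 | 5.0 |
| 75% | 1.00 | 6.7 | 9.3 | 9.3 |
| 87.5% | 1.00 | 5.7 | 10.3 | 10.3 |

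The unconditional figure is P(cross) times the conditional one, for example 0.812 × 4.83 = 3.9. With c = 6 the figures given crossing are 3.6, 4.1, 8.0 and 9.1. The result is fixed before the 16th patient with probability 76% at a true rate of 39% and 86% at 44%.

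**Step 4: reporting lag.** This was simulated with Poisson accrual. Events become known either uniformly over the 28 days or at their end (an assumption). Arm C patients avoided, given crossing and ignoring the other rules:

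| True rate | 1.5-2 per month | 5 per month |
|---|---|---|
| 39% | 3.3-4.2 | 1.5-2.9 |
| 44% | 3.8-4.9 | 1.9-3.5 |

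**Step 5: Arm B's rates with the death and perforation rules running, no lag.** Let q be the per-patient chance of a death or perforation: 0.125 if the two fully overlap, 0.25 if they never do. Count both as grade 3+ events, and treat a perforation suspension as a halt.

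- Expected Arm C accrual under the present rules is [1 − (1−q)^16]/q, which is 7.1 (q = 0.125) or 4.0 (q = 0.25).
- With the count rule added it is Σ(n = 1 to 16) Σ(j = 0 to 4) C(n−1, j)(p−q)^j (1−p)^(n−1−j).

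| p | q | Present | With count rule | Saved |
|---|---|---|---|---|
| 0.75 | 0.125 | 7.06 | 4.78 | 2.3 |
| 0.875 | 0.125 | 7.06 | 4.30 | 2.8 |
| 0.75 | 0.25 | 3.96 | 3.47 | 0.5 |
| 0.875 | 0.25 | 3.96 | 3.26 | 0.7 |

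A death or perforation comes before, or in the same patient as, the fifth event in 54-87% of cases.

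**The case against.** The strongest reply is that the plan already guards against a repeat of Arm B. Deaths and perforations halt accrual at once, and at Arm B's rates they usually do so before a count rule would. That stands, and it removes most of the apparent harm at 75-87.5%. A reader might infer that 9-10 patients would be exposed needlessly; that needs Arm B's grade 3+ rate without its deaths or perforations.

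A reader might also infer that nobody is watching. The documents do not support this: the calls include an independent monitor, grade 3-4 events get particular attention, and nothing bars earlier action. What is missing is any threshold that obliges it.

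The 16 patients also have a second purpose. Section 9.1 promises a 90% interval no wider than 44.3 points and a 56.0% chance of seeing an event of 5% frequency (81.5% at 10%). Stopping at patient 11 gives an interval up to 53 points wide and chances of 43% and 69%; stopping at patient 6 gives 69 points, 26% and 47%. So it would be wrong to say that earlier timing is the only effect. The review can still proceed on fewer patients, and accrual can resume after it.

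A running count can also fall. Attribution may change, and Section 1.6 records a duplicate registration and a never-treated case among 35. This is a reason to count verified events, not to wait for patient 16.

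Finally, a fixed-cohort look may be deliberate, since the original design in Section 9.2 also reviewed toxicity at a fixed 20 per arm. That explains the form, but gives no reason to keep enrolling once the count is met.

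**Conclusion.** The point holds, with a modest effect. The rule waits for patient 16 although its implied count of 5 can be met earlier, and no section requires suspension at that moment. At the design alternatives, ignoring the other two rules, about 4-5 Arm C patients on average would enrol after the result is fixed (3.9 and 5.0 unconditionally, no lag), or about 1.5-4.9 given crossing once lag is allowed for. At Arm B's toxicity the figure is about 0.5-2.8 with all rules running and no lag; 9-10 applies only without deaths and perforations. At the null rate the change touches only the 11.4% of cases that would have suspended anyway.

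These figures assume independent patients with a common event rate, 1:1 accrual at the planned speeds and a critical count of 5. A reader might take crossing to mean that the regimen has failed. Section 9.1 does not say so: a significant result leads to suspension and review, and only a toxic death ends the regimen automatically.

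**What to change.** State the critical count in Section 9.1 (5 of 16, if the stated power is intended) and replace the single look with: *accrual will be suspended for the feasibility review as soon as the number of Arm C patients with a verified treatment-related grade 3 or higher event, counted over the same 2-cycle evaluation window among the first 16 treated Arm C patients, reaches the critical count*. Report the running count on each scheduled call.

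The window and the 16-patient limit are essential. "At the time of suspension of this study prior to reactivation, the accrual rate was about 3-4 patients per month", so 16 Arm C patients take 16/2 = 8 to 16/1.5 ≈ 11 months. Counting events from later cycles over that time would raise the false-alarm rate above 0.114.

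The cost is a short edit plus verification of events that already reach the calls. The test's false-alarm rate and power do not change, and the review process stays as written. The one loss is a less precise toxicity estimate at the review when suspension comes early.
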